## Background and Rationale

Resistance training offers many benefits for community-dwelling elderly adults, impacting physiological, cognitive, psychological, and functional domains. Existing research highlights the importance of utilizing resistance training as an intervention to counteract age-related declines such as loss of muscle mass, decreased strength, and diminished cognitive function. The evidence indicates significant improvements in muscle mass, strength, sleep, fluid cognition, and overall quality of life, all of which contribute to enhanced functional performance and reduced risk of injury. Despite the robust findings supporting resistance training in older adults, its integration into occupational therapy practices remains underexplored. This study will aim to bridge this gap, emphasizing the occupational therapy perspective and its potential to provide holistic, person-centered resistance training interventions to improve functional performance. The utilization of compound movement resistance training within this project will establish new pathways for occupational therapy professionals to support the health and independence of community-dwelling elderly adults (Coelho-Júnior et al., 2021; Cranmer & Walston, 2022; Gupta et al., 2022; Lai et al., 2023; Macaulay et al., 2021; Marzuca-Nassr et al., 2024; Syed-Abdul et al., 2022; Voulgaridou et al., 2023).

## Specific Aims

This study aims to assess the impact of compound resistance training on the ability of adults age 65 and older to participate in desired daily activities, their satisfaction with their level of participation, and their overall mental health.

## Study Design and Procedures

This is a quasi-experimental pre-test post-test study. Following initial screening for eligibility via inclusion and exclusion criteria, and completion of informed consent discussion and signed form, subjects will complete an initial assessment. This assessment will consist of a semi-structured interview, completion of the Patient Health Questionnaire (PHQ-9) and Perceived Stress Scale (PSS), and completion of the Canadian Occupational Performance Measure (COPM) with guidance from principal investigator, who has been trained in administration of this occupational therapy field-specific assessment.

Intervention will take place over the course of 10 weeks, with individual sessions occurring twice weekly for one hour per session with each participant. Each session will consist of personalized strength training sessions, utilizing programming with a focus on compound, multi-joint movements, in keeping with existing literature on the subject. The nature of the exercises will be submitted for IRB review in a separate document (*Intervention Guide*). Each session will be designed based upon the PI's evaluation of each individual participant with customized interventions. The PI will record specific

Title: Occupational Impacts of Compound Resistance Training in Community-Dwelling Older Adults  
PI: [name]  
Institution: University of Arkansas for Medical Sciences

exercises prescribed and completed, including volume, load, and Rate of Perceived Exertion (RPE) from subject report. Ongoing reassessment will be conducted from session to session with changes made in intervention throughout. At completion of the 10-week study, subjects will complete a reassessment with the same measures from the initial assessment, the PHQ-9, the PSS, and the COPM. Subjects will also be asked to re-answer the questions from the semi-structured interview.

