## Risks and Benefits

A risk to study participants is the potential for loss of confidentiality of study data.

Measures to protect the confidentiality of study data will be implemented as described in the Data Handling and Recordkeeping section below.

Another risk to participants is injury or medical event relating to exercise.

Measures to protect subjects include adequate facilities at site of intervention, such as a well-maintained space and equipment that is regularly inspected for safety. An AED is also available in the facility. Provisions for emergency treatment available in the location also include a level 2 trauma center hospital located less than 1 mile from the facility. Appropriately qualified PI will be conducting this study, with qualifications including certification in Barbell Rehab Method and Basic Life Support CPR, as well as classroom and clinical education in occupational therapy assessment and intervention. Trained fitness professionals are also employed on site and will be present throughout the intervention.

Potential benefits include:

- Improved ability for subjects to participate in desired daily activities
- Improved mental health of subjects
- Improved physical health of subjects
- Improved subject knowledge of exercise options, safety, form, and benefits

Data safety will be monitored by the PI and reviewed every 30 days for risk trends.

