## Multisite Research

Title: Occupational Impacts of Compound Resistance Training in Community-Dwelling Older Adults  
PI: [name]  
Institution: University of Arkansas for Medical Sciences

This study has one PI. The PI is responsible for all data collection, data management/storage, protocol modification, and submission of amendments to IRB. UAMS is the Reviewing IRB. University of Arkansas Fayetteville and Washington Regional Medical Center are Relying Institutions.

Fitness professionals that will be onsite are employed by Washington Regional Medical Center. They will not be part of the research team, nor will they participate in the consent, data collection, or data analysis. Their role is strictly an added safety component of additional trained individuals present at the facility during intervention, however not involved in the study directly.

No research elements will be conducted by University of Arkansas Fayetteville or Washington Regional Medical Center entities. The PI is a student in a dual-enrolled program within both UAMS and UAF. One employee at the Washington Regional Medical Center (facility manager) will serve as a site mentor and content expert for advising the PI throughout the study, though not conducting any data collection, data analysis, or partaking in consent procedures.

The PI retains responsibility for overseeing protocol implementation, including adherence to IRB-approved protocol in intervention implementation and for maintaining all data confidentiality. PI will retain responsibility for reporting any adverse events, including data related adverse events.

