## **Data Analysis**

Data from the objective assessments conducted in this study will be analyzed using statistical analysis to determine if a clinically significant difference exists between the pre- and post-test scores for each assessment. The threshold for clinical significance is 5 points on the PHQ-9 (Kroenke et al., 1999). There is limited research published on the minimal clinically important difference (MCID) for the PSS, however it is estimated to be about 4 points (Drachev et al., 2020). In prior research with community-dwelling older adults, the MCID for the COPM was found to be 3 points for both performance and satisfaction sections (Tuntland et al., 2016).

Themes in subjective data will be coded and analyzed from identification of any changes in subjects' interviews.

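### Exercise injury is a named risk, but the protocol specifies no procedure for eliciting or recording harms and plans no harm count beside the pre/post scores

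*Combined protocol and SAP*

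**What the plan says.** Four parts of the combined protocol and SAP bear on harms.

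- **Risks and Benefits** states: "Another risk to participants is injury or medical event relating to exercise". The section ends: "Data safety will be monitored by the PI and reviewed every 30 days for risk trends". It does not say which data that review uses.
- **Study Design and Procedures** says the PI will record "exercises prescribed and completed, including volume, load, and Rate of Perceived Exertion (RPE) from subject report". The next sentence adds: "Ongoing reassessment will be conducted from session to session with changes made in intervention throughout". What that reassessment asks, and whether the answers are written down, is not stated. At the end of the 10 weeks participants repeat "the same measures from the initial assessment, the PHQ-9, the PSS, and the COPM", and answer the semi-structured interview again.
- **Multisite Research** states: "PI will retain responsibility for reporting any adverse events, including data related adverse events". No definition, time window, form or method of asking is given.
- **Data Analysis** begins: "Data from the objective assessments conducted in this study will be analyzed using statistical analysis", with the purpose "to determine if a clinically significant difference exists between the pre- and post-test scores for each assessment". Interview themes are coded as well. No tabulation of adverse events, injuries or injury-related withdrawals is planned.

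**The concern.** The protocol sets up a trend review and a duty to report, but describes no step that supplies either with systematic data. A strain, fall or symptom that appears at home between sessions reaches the PI only if the participant mentions it, or if the unspecified reassessment happens to bring it out. A participant who stops because of an injury may have no further session and no week-10 visit, and no contact with early stoppers is described. The people most informative about harm are therefore the likeliest to be missing.

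The same PI delivers the training, collects all the data and reviews safety, which makes a standard question more useful. The results may be published, and the Background cites a lower risk of injury among the gains from resistance training. A report on participation and mental health in adults aged 65 and over, with no harm count beside it, would leave the reader unable to tell whether no harm occurred or none was asked about. Dated answers to a direct question cannot be recovered once the study is over.

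**Working it through.** The plan gives no harm rate and no safety calculation, so there is no figure of its own to reproduce. The check has two parts.

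**1. Each place where harm data could enter**

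| Place | What is specified | Elicited harm item? |
|---|---|---|
| Session record | Exercises, volume, load, RPE | None named; the list is not closed |
| Session-to-session reassessment | That it takes place and leads to changes in the intervention | Content not stated |
| Week-10 reassessment | PHQ-9, PSS, COPM, interview | No injury measure; interview questions not given |
| Adverse-event duty | The PI reports events | No definition, form or method of asking |
| 30-day review | The PI looks for risk trends | Input not stated |
| Data Analysis | Pre/post scores, interview themes | No harm count |

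No row specifies that participants are asked about harm, and the last row carries no harm count into the results.

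**2. What harm data could show at this sample size**

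Inputs: 20 participants (Study Population); 10 weeks with two sessions a week (Study Design and Procedures).

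Planned exposure at full attendance: 20 × 10 × 2 = 400 sessions.

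Upper exact limit for the proportion of participants affected, with 0 events in n = 20, is 1 − α^(1/n):
- one-sided 95%: 1 − 0.05^(1/20) = 13.9%
- two-sided 95%: 1 − 0.025^(1/20) = 16.8%

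Exact (Clopper-Pearson) two-sided 95% intervals for small counts:
- 1 of 20 (5%): 0.1% to 24.9%
- 2 of 20 (10%): 1.2% to 31.7%

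Chance of at least one affected participant among 20, with true risk p, is 1 − (1 − p)^20. The documents give no rate, so p is an assumption shown over a range:
- p = 5%: 1 − 0.95^20 = 64%
- p = 10%: 1 − 0.90^20 = 88%
- p = 20%: 1 − 0.80^20 = 99%

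These figures show what a systematic question could deliver. They do not measure how many events the present plan would miss, which cannot be derived from the documents.

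**The case against.** The strongest reply is that harm information is not absent from this study. The PI must report adverse events, sees each participant individually twice a week, reassesses from session to session and also conducts the 30-day review, so any event known to the PI is known to the reviewer. That stands, and it rules out several stronger conclusions that a reader might infer:

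- *That the review has no harm data, or that participants are never asked.* The reporting duty and the reassessment both allow harm information to reach the PI. The content of the reassessment is unstated, and silence does not show that the question is not put.
- *That the session record excludes injury.* The list is introduced by the word *including*. The word follows the exercises prescribed and completed, so it most naturally admits further exercise detail, but it does not close the record.
- *That the outcomes can show only benefit.* PHQ-9, PSS and COPM scores can worsen, and the interview coding covers change in either direction. An injury that limits daily activity might show in the COPM or the interview. None of these, however, is a dated record of injury.
- *That the 30-day review is certainly an injury review.* The phrase about data safety could refer to data security, since confidentiality is the first risk in that section. If that is the meaning, this protocol contains no periodic review of injuries at all, and the gap is wider.

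It is also fair that the protocol states no safety aim, that the separate Intervention Guide is not available here, and that institutional policies may add requirements. The guide is described as covering the nature of the exercises, so it may not deal with safety data. The point is therefore limited to what this protocol specifies.

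**Conclusion.** The point holds as a gap in specification. Adverse events are to be reported and risk trends reviewed, but this protocol does not define the events, say how they are elicited and recorded, or plan to report them with the results. Capture would depend mainly on what is seen or volunteered.

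Its size is moderate. With 20 participants, even perfect collection with no events would leave a risk of about 14% (one-sided) or 17% (two-sided) not excluded, so the study could not establish safety. It could give an honest count, and if the true risk per participant were between 5% and 20%, at least one affected participant would be expected with probability 64% to 99%. These figures assume that all 20 participants start training, are all followed for harms, and are independent of one another; the 400 sessions assume full attendance. This is a worthwhile, inexpensive improvement and does not undermine the pre/post comparison.

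**What to change.** - **Study Design and Procedures.** Add one dated item to each session record and to the week-10 reassessment, asking about any new injury, fall, medical event or pain since the last contact. Record whether it is related to exercise and whether a session was changed or missed because of it. Record expected muscle soreness separately from injury. Ask participants who stop early for their reason, and put the same item to them.
- **Risks and Benefits.** State that the 30-day review covers participant safety and uses this item.
- **Data Analysis.** Report the number of participants and the number of sessions with an exercise-related injury or medical event, among all who started training. Give an exact confidence interval for the participant proportion. Report the session figure as a count, because sessions within one person are not independent.

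Cost: about a minute per session on a record the PI already keeps, a brief contact with anyone who stops early, and one descriptive table. The downside is that direct questioning finds more than unsolicited reporting, so the harm count will look less favourable. Keeping soreness separate limits this.

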## **Study Population**

20 participants will be enrolled in this study. Up to 60 individuals may engage in the consent process to obtain 20 participants in the research activities.

### **Inclusion Criteria**

- Adult age 65 or older
- Living independently in a community dwelling, such as a house or apartment
- Able to complete basic daily tasks (i.e. dressing, toileting, transfers) without assistance from another person
- Access to transportation to and from sessions for this study
- Able to attend two, one-hour sessions per week for the duration of the study
- Has a membership to Silver Sneakers, Silver and Fit, and/or Renew Active, or are willing to obtain a paid membership to Washington Regional Center for Exercise

### **Exclusion Criteria**

- Personal history of stroke or heart attack
- Limb amputation
- Heart failure or arrhythmias
- Presence of brain or aortic aneurism
- Active cancer
- Major illness
- Physical activity contraindicated as instructed by a physician
- Active drug abuse
- Moderate to severe cognitive impairment

Potential subjects will be located in the following ways:

- Handing out and/or posting fliers in community settings such as churches, local senior centers, and/or other public places such as grocery stores or shopping malls
- Advertising on social media platforms (Instagram and Facebook)

Title: Occupational Impacts of Compound Resistance Training in Community-Dwelling Older Adults  
PI: [name]  
Institution: University of Arkansas for Medical Sciences

In some cases, potential subjects will respond to posted fliers. In these cases, initial contact with the study team will be made by the subject via phone or email.

## Risks and Benefits

A risk to study participants is the potential for loss of confidentiality of study data.

Measures to protect the confidentiality of study data will be implemented as described in the Data Handling and Recordkeeping section below.

Another risk to participants is injury or medical event relating to exercise.

Measures to protect subjects include adequate facilities at site of intervention, such as a well-maintained space and equipment that is regularly inspected for safety. An AED is also available in the facility. Provisions for emergency treatment available in the location also include a level 2 trauma center hospital located less than 1 mile from the facility. Appropriately qualified PI will be conducting this study, with qualifications including certification in Barbell Rehab Method and Basic Life Support CPR, as well as classroom and clinical education in occupational therapy assessment and intervention. Trained fitness professionals are also employed on site and will be present throughout the intervention.

Potential benefits include:

- Improved ability for subjects to participate in desired daily activities
- Improved mental health of subjects
- Improved physical health of subjects
- Improved subject knowledge of exercise options, safety, form, and benefits

Data safety will be monitored by the PI and reviewed every 30 days for risk trends.

## Data Handling and Recordkeeping

The Principal Investigator will carefully monitor study procedures to protect the safety of research subjects, the quality of the data and the integrity of the study.

Names will be coded in recorded data, with the key to the code kept separately. Each participant will be identified by a number (e.g. "Participant 2") in all recorded data. The key linking the recorded data to the participants will be destroyed at the end of the study. Data will be stored via UAMS-monitored database, UAMS BOX, and made accessible only to the PI and Sub-Investigator.

At the conclusion of the study, the data will be retained for 7 years in UAMS BOX according to UAMS administrative policy before destruction.

## Multisite Research

Title: Occupational Impacts of Compound Resistance Training in Community-Dwelling Older Adults  
PI: [name]  
Institution: University of Arkansas for Medical Sciences

This study has one PI. The PI is responsible for all data collection, data management/storage, protocol modification, and submission of amendments to IRB. UAMS is the Reviewing IRB. University of Arkansas Fayetteville and Washington Regional Medical Center are Relying Institutions.

Fitness professionals that will be onsite are employed by Washington Regional Medical Center. They will not be part of the research team, nor will they participate in the consent, data collection, or data analysis. Their role is strictly an added safety component of additional trained individuals present at the facility during intervention, however not involved in the study directly.

No research elements will be conducted by University of Arkansas Fayetteville or Washington Regional Medical Center entities. The PI is a student in a dual-enrolled program within both UAMS and UAF. One employee at the Washington Regional Medical Center (facility manager) will serve as a site mentor and content expert for advising the PI throughout the study, though not conducting any data collection, data analysis, or partaking in consent procedures.

The PI retains responsibility for overseeing protocol implementation, including adherence to IRB-approved protocol in intervention implementation and for maintaining all data confidentiality. PI will retain responsibility for reporting any adverse events, including data related adverse events.

## **Data Analysis**

Data from the objective assessments conducted in this study will be analyzed using statistical analysis to determine if a clinically significant difference exists between the pre- and post-test scores for each assessment. The threshold for clinical significance is 5 points on the PHQ-9 (Kroenke et al., 1999). There is limited research published on the minimal clinically important difference (MCID) for the PSS, however it is estimated to be about 4 points (Drachev et al., 2020). In prior research with community-dwelling older adults, the MCID for the COPM was found to be 3 points for both performance and satisfaction sections (Tuntland et al., 2016).

Themes in subjective data will be coded and analyzed from identification of any changes in subjects' interviews.

## **Ethical Considerations**

This study will be conducted in accordance with all applicable government regulations and University of Arkansas for Medical Sciences research policies and procedures. This protocol and any amendments will be submitted and approved by the IRB as required.

There will be no compensation for subjects for participation in this study.

Title: Occupational Impacts of Compound Resistance Training in Community-Dwelling Older Adults  
PI: [name]  
Institution: University of Arkansas for Medical Sciences

The informed consent of each subject, using IRB-approved consent materials, will be obtained before that subject begins any study procedures. All subjects for this study will be provided a consent form on paper describing this study in language understandable to the study population. Consent materials will provide sufficient information for subjects to make an informed decision about their participation in this study. The person obtaining consent will thoroughly explain what the subjects need to know about the study, including study requirements, study risks and benefits. The consent process will take place in person at the facility prior to beginning initial session, on the same day or up to several days prior to the start of the study. Participation privacy will be maintained and questions regarding participation will be answered. No coercion or undue influence will be used in the consent process. This consent form must be signed by the subject, and the person obtaining the consent. The participant will receive a paper copy of the signed consent form, and the informed consent process will be documented in the research record.

The consent process will be documented separately via a written note in the research for each subject.

